### **ECG**

Summary statistics will be presented for ECG variables by visit and treatment group.

## **Physical development**

Growth and weight changes will be summarised descriptively.

[REDACTED]

[REDACTED].

### **9.5.3 Resource utilization**

Not applicable

### **9.5.4 Health-Related Quality of Life**

#### **Children's Dermatology Quality of Life Index (CDLQI)**

Seven scores will be derived from the CDLQI: the total score of each of the six dimensions (symptoms and feeling, leisure, school or holidays, personal relationships, sleep, treatment) as well as the total score over all items. The higher the score, the more quality of life is impaired.

For each of the seven scores the percentage change from baseline will be derived. Summary statistics will be provided for absolute values as well as for the percentage change by visit and treatment group in contingency tables .(LOCF).

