## 2 Study objectives and endpoints

### 2.1 Objectives and related endpoints

**Table 2-1 Objectives and related endpoints**

Objective(s)	Endpoint(s)
Primary Objective(s)	Endpoint(s) for primary objective(s)
To evaluate the efficacy of secukinumab in pediatric subjects aged 6 years to less than 18 years old with moderate to severe chronic plaque psoriasis with respect to PASI 75 and IGA mod 2011 0 or 1 response (co-primary endpoints) at Week 12, compared to placebo (historical control).	Proportion of subjects who achieved PASI 75 and IGA mod 2011 0 or 1 response at Week 12 in each secukinumab treatment group (low dose and high dose). Placebo data are obtained from adult secukinumab placebo-controlled trials and pediatric placebo-controlled trials with secukinumab or other biologics
Secondary Objective(s)	Endpoint(s) for secondary objective(s)
To evaluate the efficacy of secukinumab in pediatric subjects with respect to PASI 90 at Week 12, compared to placebo (historical control).	Proportion of subjects who achieved PASI 90 response at Week 12 in each secukinumab treatment group (low dose and high dose). Placebo data are obtained from adult placebo-controlled trials and pediatric placebo-controlled trials
To investigate the clinical safety and tolerability of secukinumab as assessed by growth, weight gain, vital signs, clinical laboratory variables, ECGs, and adverse event monitoring	Height and weight, vital signs, laboratory evaluations, ECG and adverse events
To evaluate the pharmacokinetics of secukinumab in pediatric subjects	Secukinumab concentration in serum at various time points
Exploratory Objective(s)	Endpoint(s) for exploratory objective(s)
To investigate the effects of treatment with secukinumab with respect to changes in CDLQI over time up to End of Treatment	Absolute and percentage change from baseline of CDLQI score over time up to End of Treatment
To investigate the effects of treatment with secukinumab with respect to CDLQI 0 or 1 score over time, up to End of Treatment	Proportion of subjects achieving CDLQI 0 or 1 over time up to End of Treatment

[figure not shown]
Exploratory Objective(s)	Endpoint(s) for exploratory objective(s)
To investigate the development of immunogenicity against secukinumab	Development of anti-Drug Antibodies (ADA) to secukinumab

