## **6.6 Other assessments**

### **6.6.1 Clinical Outcome Assessments (COAs)**

#### **6.6.1.1 Subject/Patient Reported Outcomes (PRO)**

The impact of psoriasis on various aspects of subject's health-related quality of life (HRQoL) will be assessed by Children's Dermatology Life Quality Index (CDLQI).

The Children's Dermatology Life Quality Index ([Lewis-Jones and Finlay 1995](#)) is a 10-item general dermatology disability index designed to assess health-related quality of life in pediatric subjects aged 4 to 16 years. It is self-explanatory and may be completed by the child with assistance from parents or caregivers as necessary. The 10 questions cover six areas of daily activities including symptoms and feelings, leisure, school or holidays, personal relationships, sleep and treatment. The questions are based on the preceding week to permit accurate recall.

Each question is answered on a 4-point Likert scale scored from 0 to 3. These are added to give a minimum score of 0 and maximum score of 30. A higher CDLQI score indicates greater degree of QoL impairment.

CDLQI is available in two versions, text only and text with cartoons. The text only version will be used in this study. The mean completion time of the text version is 120 seconds.

This questionnaire should be completed in the language the subject is most familiar with before any other clinical assessments,

All subjects will complete the PRO questions via an electronic tablet. The questionnaire should be completed by the subject with the help of parent/custodian if and as needed. The site staff may help understand the questions, as necessary. The subject should be given sufficient space and time to complete the questionnaire. If subject experiences any difficulties with submission after they complete the PROs, the study staff should assist with submitting the PRO responses. Attempts should be made to collect responses to all PROs for all subjects, including from those who prematurely discontinue prior to the study evaluation completion visit, however, if subjects/subjects refuse to complete PROs, this should be documented in study source records. Subject's refusal to complete study PROs are not protocol deviations.

The study coordinator should check the questionnaire for completeness and encourage the subject to complete any missing responses before the clinical examination. Missing data will not be imputed.

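### Percentage change from baseline is a poor summary for the six CDLQI dimension scores, because it is undefined for a child who scores 0 on that dimension at baseline

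*Protocol*

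**What the plan says.** Protocol 9.5.4 sets out the derived scores: "Seven scores will be derived from the CDLQI: the total score of each of the six dimensions", plus the total over all items. It then says: "For each of the seven scores the percentage change from baseline will be derived". The next sentence reads: "Summary statistics will be provided for absolute values as well as for the percentage change by visit and treatment group".

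Protocol 6.6.1.1 describes the instrument: "The 10 questions cover six areas of daily activities", and "Each question is answered on a 4-point Likert scale scored from 0 to 3". On the total it says: "These are added to give a minimum score of 0 and maximum score of 30".

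Table 2-1 lists two exploratory CDLQI endpoints: "Absolute and percentage change from baseline of CDLQI score over time up to End of Treatment" and "Proportion of subjects achieving CDLQI 0 or 1 over time up to End of Treatment".

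The severity criterion in Protocol 4.1 uses PASI, IGA mod 2011 and BSA. It sets no CDLQI threshold. Protocol 3.4 uses historical placebo data as the control for the primary and key secondary endpoints only, so CDLQI is summarised in two active arms with no comparator.

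Both SAP versions pass from 2.6.3 directly to 2.8. The document history places the other efficacy endpoints in section 2.7, which is not in the public text.

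**The concern.** A percentage change divides by the baseline value. For a dimension with one or two items, a baseline of 0 is a plausible answer: a child can have extensive plaques and still report no problem with sleep, for example. No percentage change exists for that child on that dimension.

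If the summary is limited to children with a baseline above 0, it is conditional on impairment at baseline. The children left out can only stay at 0 or get worse, while those kept in include anyone whose baseline was high by chance. Without a comparator, neither this selection nor regression to the mean is subtracted out.

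At stake is how the dimension-level quality-of-life results read. No confirmatory result is involved.

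**Working it through.** **Inputs from the documents.** Ten items, six dimensions, each item 0 to 3 (Protocol 6.6.1.1); no CDLQI entry threshold (Protocol 4.1); 40 children per arm (Protocol 9.8). The documents give no baseline CDLQI distribution.

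**1. Scale range.** 10 × 0 = 0 and 10 × 3 = 30, which reproduces the stated range.

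**2. Number of single-item dimensions.** Let k of the six dimensions have one item and the others at least two. Then k + 2(6 − k) ≤ 10, so k ≥ 2. At least two dimension scores run only from 0 to 3.

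**3. The ratio on such a dimension.** Percentage change = 100 × (post − baseline)/baseline.
- Baseline 0: undefined.
- Baseline 1: −100, 0, +100 or +200%.
- Baseline 2: −100, −50, 0 or +50%.
- Baseline 3: −100, −67, −33 or 0%.

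One child moving from 1 to 3 (+200%) offsets two who clear (−100% each), so the mean is also unstable.

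**4. Effect of leaving out the zero-baseline children (assumed inputs).** Let p0 be the share at 0 at baseline, m the mean percentage change in the rest, and c ≥ 0 the value given to the zero-baseline children. The mean over all children is (1 − p0)m + p0·c. With c = 0 (no change), the gap from m is p0 × |m|. If m < 0, this is the smallest possible gap, since a larger c widens it.

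| p0 | Children with a ratio, of 40 | m = −50%: all-children mean (gap) | m = −70%: all-children mean (gap) |
|---|---|---|---|
| 10% | 36 | −45% (5) | −63% (7) |
| 20% | 32 | −40% (10) | −56% (14) |
| 30% | 28 | −35% (15) | −49% (21) |
| 40% | 24 | −30% (20) | −42% (28) |
| 50% | 20 | −25% (25) | −35% (35) |

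The gap runs from 5 to 35 percentage points over this assumed range.

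**5. Is the direction fixed?** Take a single 0–3 item with no true change: baseline B and follow-up are independent with the same distribution and mean μ. Mean absolute change over all children is then 0. Among children with baseline above 0, mean percentage change is 100 × (μ × E[1/B | B > 0] − 1).

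| Assumed shares at 0, 1, 2, 3 | Mean % change, baseline > 0 |
|---|---|
| .25, .25, .25, .25 | −8.3% |
| .4, .3, .2, .1 | −27.8% |
| .5, .3, .15, .05 | −41.2% |
| .2, .4, .3, .1 | −5.2% |
| .1, .5, .3, .1 | +6.3% |

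For the third row, μ = 0.75 and E[1/B | B > 0] = 0.6 + 0.3/2 + 0.1/3 = 0.7833. The product is 0.5875, which gives about −41%. The last row is positive because rises from 1 count as +100% or +200%. Four of the five cases show an apparent improvement where there is none, and one shows an apparent worsening.

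**The case against.** The strongest reply is that little depends on this. CDLQI is exploratory and descriptive, with no test in the visible text. Protocol 9.5.4 also summarises absolute values by visit and arm. These are defined at a baseline of 0, so every child stays in and a worsening from 0 counts. Table 2-1 names absolute change and the proportion scoring 0 or 1, and neither divides by baseline. SAP 2.1 gives n, median and quartiles for continuous variables, so a smaller n would show and the mean is not the only statistic. All of this stands, and it limits the point to the percentage-change summaries. Two gaps remain: absolute values by visit are not within-child change, and n alone does not separate a zero baseline from a missing value.

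A reader might infer that the plan drops these children without saying so. The documents do not support that. No visible text says they are dropped, and section 2.7 or the project standard analysis plan cited in SAP 2.1 may hold a rule. It therefore cannot be claimed that a rule is missing. The point does not need that claim: any rule must either exclude these children or give them a value that the ratio does not have.

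A reader might also infer that improvement is necessarily overstated. That goes too far, as the +6.3% case shows. Overstatement relative to an all-children mean follows if the remaining children improve on average, and its size depends on a baseline distribution that the documents do not give.

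**Conclusion.** The point holds in a limited form, with low severity. Percentage change is planned for all six dimension scores, at least two of these are single 0–3 items, and nothing at entry prevents a baseline of 0. For such children the ratio is undefined. A summary limited to baseline above 0 can overstate improvement, with no comparator to correct it.

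The figure of 5 to 35 percentage points rests on three assumptions: 10–50% of children at 0 on the dimension, a mean change of −50% to −70% in the rest, and zero-baseline children counted as unchanged. It illustrates the possible scale and is not an estimate for this trial. The co-primary endpoints, PASI 90 and the safety analyses are unaffected.

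**What to change.** For the six dimension scores, replace percentage change with within-child absolute change from baseline, using all children with both values. Table 2-1 already names absolute change for CDLQI, so this also brings 9.5.4 into line with it. Keep percentage change for the total score only, among children with a total above 0 at baseline, and print the number excluded for a zero baseline by arm and visit. If section 2.7 already has a zero-baseline rule, check it against this and cite it.

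The cost is a sentence in the protocol or SAP and one changed derivation, with no new data. The downside is that dimension results no longer appear as percentages.

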### **9.5.5 Pharmacokinetics**

All completed subjects with quantifiable pharmacokinetic (PK) measurements of secukinumab will be included in the pharmacokinetic data analysis. Serum concentrations will be expressed in mass per volume units. All concentrations below the limit of quantification or missing data will be labeled as such in the concentration data listings. PK concentrations will be summarized by visit and treatment group. In addition to mean, standard deviation, coefficient of variation, median and quartiles, the geometric mean and geometric coefficient of variation and n(log) will be presented.

### **9.5.6 DNA**

Not Applicable.

### **9.5.7 Biomarkers**

Not applicable

### **9.5.8 PK/PD**

Not applicable

## **9.6 Analysis of exploratory variables**

The following exploratory efficacy endpoints will be assessed:

[REDACTED]

[figure not shown]
## **PASI 75, PASI 90, PASI 100 and IGA 2011 0 or 1 response over time**

Number of subjects with PASI 75, PASI 90, PASI 100 and IGA mod 2011 0 or 1 response by treatment and visit will be presented in frequency contingency tables and will include absolute and relative frequencies.

Figures will be provided displaying responder rates by treatment including confidence intervals.

## **PASI score over time**

Summary statistics will be provided for absolute PASI scores as well as for percent change from baseline by treatment and visit. Figures will also be provided.

## **9.7 Interim analyses**

There are two planned interim analysis. An interim analysis of the data collected up until Week 16, including the co-primary endpoint (at Week 12) will be performed after all subjects have completed either their Week 16 visit or the premature treatment discontinuation visit. Another interim analysis will be performed when all subjects have completed the Week 52 visit, (or premature treatment discontinuation visit).

Additional analyses may be performed to support health authority interactions, as necessary.

Thereafter, efficacy and safety data collected after Week 52 until the end of study may be reported yearly in separate reports.

Trial modifications are not planned based on any interim analysis.

## **9.8 Sample size calculation**

The sample size for this study is calculated to ensure an adequate number of subjects for PK analyses and powered efficacy analyses. Approximately 80 pediatric subjects from 6 to less than 18 years of age at randomization will be recruited. Since a 15% screening failure rate is

expected, approximately 95 patients will be screened. The study will aim to recruit at least 60 subjects with moderate severity and approximately 20 subjects with severe severity.

Power calculations were performed to support the co-primary endpoints PASI 75 and IGA 0 or 1 response at week 12, and secondary endpoint PASI 90 at week 12, versus placebo (historical control) for the low and high secukinumab dose regimens. Data from four adult placebo-controlled trials (CAIN457A2302, CAIN457A2303, CAIN457A2308 and CAIN457A2309) and pediatric placebo controlled trials ([Paller et al 2008](#), [Landells et al 2015](#)) were used to estimate the historical placebo response rate. For study CAIN457A2310, a 10% response rate was assumed for PASI 75, IGA 0 or 1 and PASI 90 response for the placebo group. The power calculation was performed assigning pediatric data moderate heterogeneity and adult trial data substantial heterogeneity ([Neuenschwander et al.2010](#)), thus allowing pediatric trial data to be given twice the weight compared to adult trial data. All the calculations were performed in the R package RBesT (version 1.1) through the meta-analytical-predictive framework ([Spiegelhalter et al. 2004](#), [Neuenschwander et al. 2010](#)), and the predicted response rate of the placebo group for this study are presented in [Table 9-2](#) below by endpoint.

**Table 9-2 Predictive placebo response rates for this study from model of historical data**

Endpoint	Mean	Standard Deviation	Median	95% CI
IGA 0 or 1	9%	6%	8%	1-23%
PASI 75	10%	6%	9%	2-25%
PASI 90	6%	4%	5%	1-18%

Requiring that the posterior probability of the log odds ratio difference between placebo and secukinumab exceeds with at least 97.5% zero leads to a power of approximately 99% for each co-primary endpoint when assuming a sample size of 40 pediatric patients per treatment group and true response rates of 10% and 65% for PASI 75 and 9% and 45% for IGA mod 2011 0 or 1 response for placebo and secukinumab respectively.

For the secondary endpoint of PASI 90 response, assuming a response rate of 6% and 39% for placebo and secukinumab respectively, the power to provide a posterior probability of at least 97.5% that the PASI 90 response rate on secukinumab is greater than placebo at week 12 is approximately 99%.

The assumed response rates for secukinumab are based on confirmatory efficacy in the adult phase III program (CAIN457A2302, CAIN457A2303, CAIN457A2308 and CAIN457A2309).

## 10 Ethical considerations

### 10.1 Regulatory and ethical compliance

This clinical study was designed and shall be implemented, executed and reported in accordance with the ICH Harmonized Tripartite Guidelines for Good Clinical Practice, with applicable local regulations (including European Directive 2001/20/EC, US CFR 21, and Japanese

Ministry of Health, Labor, and Welfare), and with the ethical principles laid down in the Declaration of Helsinki.

## 10.2 Informed consent procedures

Eligible patients may only be included in the study after providing written (witnessed, where required by law or regulation), IRB/IEC-approved informed consent, or, if incapable of doing so, after such consent has been provided by a legally acceptable representative(s) of the patient. In cases where the patient's representative gives consent, the patient should be informed about the study to the extent possible given his/her understanding. If the patient is capable of doing so, he/she should indicate assent by personally signing and dating the written informed consent document or a separate assent form. Informed consent must be obtained before conducting any study-specific procedures (i.e. all of the procedures described in the protocol). The process of obtaining informed consent should be documented in the patient source documents.

Novartis will provide to investigators in a separate document a proposed informed consent form that complies with the ICH GCP guideline and regulatory requirements and is considered appropriate for this study. Any changes to the proposed consent form suggested by the investigator must be agreed to by Novartis before submission to the IRB/ IEC, and a copy of the approved version must be provided to the Novartis monitor after IRB/IEC approval.

In pediatric patients (< 18 years of age) parental permission and, whenever possible, child assent is needed instead of the procedure for informed consent used for research involving adults. In general, one or both parents or a guardian must be provided with the information ordinarily required for informed consent, so that they may decide whether to allow the child to participate, and children capable of assent must also express their willingness to participate. These forms will be submitted for IRB/IEC/REB approval. Subjects who turn 18 years of age during the trial must sign the general informed consent form.

Women of child bearing potential should be informed that taking the study treatment may involve unknown risks to the fetus if pregnancy were to occur during the study and agree that in order to participate in the study they must adhere to the contraception requirement for the duration of the study. If there is any question that the patient will not reliably comply, they should not be entered in the study.

In the event that Novartis wants to perform testing on the samples that are not described in this protocol, additional Institutional Review Board and/or Ethics Committee approval will be obtained.

During the COVID-19 pandemic or similar major health care disruption that may challenge the ability to obtain a standard written informed consent due to limitations that prevent an on-site visit, the Investigator may conduct the informed consent discussion remotely (e.g. telephone, videoconference). Guidance issued by local regulatory bodies on this aspect prevails and must be implemented and appropriately documented (e.g. the presence of an impartial witness, sign/dating separate ICFs or assent forms by trial subject/ guardian and person obtaining informed consent, etc).

In case Home Nursing (other than study treatment administration) is implemented during the COVID-19 pandemic or similar major health care disruption, a separate Home Nursing informed consent document must be used in addition to the study ICF.

### **10.3 Responsibilities of the investigator and IRB/IEC**

Before initiating a trial, the investigator/institution must obtain approval/favorable opinion from the Institutional Review Board/Independent Ethics Committee (IRB/IEC) for the trial protocol, informed consent form, consent form updates, subject recruitment procedures (eg, advertisements) and any other written information to be provided to subjects/subjects. Prior to study start, the investigator is required to sign a protocol signature page confirming his/her agreement to conduct the study in accordance with these documents and all of the instructions and procedures found in this protocol and to give access to all relevant data and records to Novartis monitors, auditors, Novartis Quality Assurance representatives, designated agents of Novartis, IRBs/IECs, and regulatory authorities as required. If an inspection of the clinical site is requested by a regulatory authority, the investigator must inform Novartis immediately that this request has been made.

### **10.4 Publication of study protocol and results**

The key design elements of this protocol will be posted in a publicly accessible database such as clinicaltrials.gov. In addition, upon study completion and finalization of the study report the results of this trial will be either submitted for publication and/or posted in a publicly accessible database of clinical trial results.

### **10.5 Quality Control and Quality Assurance**

Novartis maintains a robust Quality Management (QM) system that includes all activities involved in quality assurance and quality control, including the assignment of roles and responsibilities, the reporting of results, and the documentation of actions and escalation of issues identified during the review of quality metrics, incidents, audits and inspections.

Audits of investigator sites, vendors, and Novartis systems are performed by Novartis Pharma Auditing and Compliance Quality Assurance, a group independent from those involved in conducting, monitoring or performing quality control of the clinical trial. The clinical audit process uses a knowledge/risk based approach.

Audits are conducted to assess GCP compliance with global and local regulatory requirements, protocols and internal SOPs, and are performed according to written Novartis processes.

